15 minutes). Trend arrows (rising, rapidly rising and falling and rapidly falling), will be taken into consideration looking at the whole patient picture, including nutritional intake and timing of meals/medications. When CGM alarms, "Followers" (which may include research staff and/or tele tech staff) will alert nursing staff assigned to the patient to conduct POC testing and treat patient accordingly per Research (PFO) or Hospital protocol (whichever applies).

For Type 2 patients randomized to the Control group, blood glucose values from CGM are not visible by APN or tele tech staff. PFO will still apply during any time patient gets a POC from bedside RN per standard hospital procedures.

Sensor Removal:

The sensor will be removed before hospital discharge, at day 10 post insertion, if the sensor fails for any reason or if the patient is to undergo a CT or MRI procedure. The sensor may also be removed at the discretion of the Principal Investigator. If the patient is to continue hospitalization, then a new sensor will be inserted. Once a sensor is removed, the insertion site will be examined for any inflammation/bleeding.

Follow-up:

A follow-up questionnaire will take place within 7 days from discharge (including discharge date) to assess any adverse events and to obtain patient satisfaction data regarding his/her hospital stay and use of the CGM device.

Provider satisfaction data will also be gathered (via focus group or questionnaire) after study patients have been discharged.

Measurements and Analysis

Clinical measures: Clinical measures that will be collected will include HbA1c on admission and at any time post admission while the patient is hospitalized, point of care glucose values conducted with the hospital based glucose meters (a minimum of four times a day) and CGM downloaded data. The reason for admission and patient medical history will be collected from the patient records.

Any change in insulin dosing per APN and/or physician will be collected.

Medications: All diabetes medication, steroids and acetaminophen use will be recorded.

Behavioral measures: Patient satisfaction surveys will be collected just prior to discharge and/or one week post discharge to assess the experience with the hospital based CGM device and glucose management. Post discharge 2 patient focus groups will be convened with a minimum of 5 patients in each group to assess patients experience and recommendations after participating in the pilot. Two additional focus groups will be convened with providers that include staff nurses, hospitalists and advanced practice nurses from the glucose management team to gather level of satisfaction and recommendations based on their experience.

Data analysis: (See Appendix C for Statistical Analysis Plan)

Potential Risks

The procedure of insertion and retraction of the needle and the sensor placement itself may cause redness, edema, and/or bruising at the site of insertion. Local infection at insertion site, erythema, inflammation, bleeding, or hematoma are also possible. The frequency of these last events is very low.

Once the sensor is removed, irritation at the site may be present. This may be due to the adhesive (MARSI or Medical Adhesive Related Skin Injuries). This reaction should resolve within a few days to a week. Patients may experience itching at the area which is normal as part of the healing process. These possible expected risks will be assessed with the 1 week f/u call.

There is a remote chance that the sensor or introducer needle could break if insertion is performed improperly. A minor procedure similar to removing a splinter may be required to retrieve the fragment. To minimize the risk associated with this procedure, only trained personnel will perform the insertion of the sensor.

Rarely participants may develop an allergic reaction to any component of the sensor and/or transmitter. This is similar to allergies that occur due to medical tape. If this occurs, then the device will be withdrawn and the patient will be discontinued from participation.

Fingersticks are part of regular patient care. An increased number of fingersticks may take place if the CGM values are not within goal or if there are downward or upward rate of change arrows. Fingersticks may cause pain and/or a bruise.

Hypoglycemia and/or hyperglycemia may occur during the course of the study. Hypoglycemia may be associated with reduced cognitive, diaphoresis, tachycardia, coma and seizure. Symptoms of hyperglycemia may be associated with thirst, glycosuria, ketoacidosis, and hyperosmolar coma. The risk of these complications is an inherent risk of having diabetes. Close follow-up during patient participation will minimize these risks.

Patient blood glucose information will be viewed by specific Scripps staff. The creation of Dexcom share accounts will be established by Scripps research staff. No patient information will be entered within the apps. All info will be coded.

All research staff will complete human subjects' research training prior to their involvement. There are no other known risks.

All data collected are for research purposes only and findings will be presented only in aggregate form. No identifiable information on individuals will be used in reports or manuscripts. To ensure confidentiality, data will be kept in locked files when not in use and will be properly stored at the Scripps Whittier Diabetes Institute. Participants will be assigned identification numbers for data management and data will be identified only by these numbers. A master list of identification numbers, names, and contact information will be kept separate from data in a locked file cabinet at the Scripps Whittier Diabetes and/or in a secure file. This list will never be stored with the participants' data, and will be accessible only to the investigators and trained project assistants.

Study records will be stored in the clinical trials office at Scripps Whittier Diabetes Institute.

Potential Benefits

The anticipated potential benefit in joining the study includes improved glucose management during hospitalization with decreased incidence of hypo and hyperglycemic events. The patient may also learn more about self-diabetes management while participating in the study. However, there is no guarantee that participants will incur any personal benefit from participating in the study. The information learned from this study may help improve the way diabetes is managed within a hospital setting.

Adverse Events (AE):

Overview of rating severity and relationship of AE to Study Device: An adverse event is an event that was not present when the patient was consented. The event can be an acute event, like cough or cold symptoms or worsening of symptoms (in this case an example would be recurrent MI after the patient was admitted for an MI). For study purposes, adverse events will be collected in relation to CGM device use. Serious adverse event can include a significant medical event (ie. severe hypoglycemia, etc).

PI or sub-I will determine the relationship of the AE to CGM use and/or APN-S as not related, possibly related or probably related. Information regarding action taken (none, CGM interrupted, CGM discontinued, or none, APN-S interrupted, APN-S discontinued) will also be collected. Severity (mild, moderate, severe) and outcome (resolved, resolved with sequelae, ongoing, death)

will also be assessed. Information regarding the use of a medication for the AE will also be collected.

Adverse Device Effect (ADE): May include redness, bruising, etc. May also include malfunction of the sensor, transmitter, phone or Dexcom share. AE charting will be done as above.

Serious Adverse Device Effect (SADE): If the PI or sub-I find the ADE to be serious, then the event will go under SADE. AE charting will be done as above.

Serious Unexpected Adverse Device Event (SUADE): If the PI or sub-I find the ADE to be serious and unexpected, then the event will go under SUADE. AE charting will be done as above.

Serious Adverse Event (SAE): Any event of severe hypoglycemia (an episode requiring assistance of another person to actively administer carbohydrate, glucagon, or take other corrective actions) will be collected. Any significant medical event will also be collected.

Confidentiality Procedures

Data to be published or made public will not contain any identifying information. Demographic information will be seen only by the research staff and individuals managing the patient health during hospitalization. The participants will be assigned an identifying number, instead of their names, to ensure their privacy. All data will be transported in locked boxes to the clinical research office at Scripps Whittier Diabetes Institute, where these items and the rest of the study files will be stored in a locked office. The study researchers and their research team, sponsoring agency, government research agencies, and the Scripps IRB are the only ones allowed access to any information from this study. The documents obtained in relation to and during the study will be held for 7 years after study completion. Data that may be entered in databases will be kept in Scripps encrypted computer systems. All data will be de-identified for analyses. If data is to be transferred to any of the facilities specified above, it will be de-identifiable data.

Costs to Subjects

Participants will not incur any cost for participation.

Compensation

Participants will not receive any compensation as part of study participation.

Timeline

Study implementation steps	- 3 months	0 months	0 – 5 months	0 - 60 months	60	60 – 70 months
Obtain CGM Share						
Direct devices, sensors	X					
and transmitters						
Train hospital glucose						
management teams and						
telemetry monitoring	X					
teams in device						
placement and protocol						
Introduce devices and						
protocol to hospital RN	X					
and MD staff						
Begin patient enrollment,						
consenting and data		v				
safety and monitoring						
(each hospital enrollment may start at different		X				
times)						

[figure not shown]
Pilot enrollment and data		X			
gathering					
Ongoing data safety and			X		
monitoring review			Λ		
Patient enrollment ends				X	
Data compilation from					
the electronic data			X		
warehouse					
Data analysis			X		X
Patient and provider			X		X
focus groups			Λ		Α
Final report &					v
Dissemination of results					X

References

- 1. Qual. Safe Health Care. 2008, Dec;17 (6): 464-8.- Health systems are integrating approaches to care to improve quality and financial goals
- 2. Kavanagh & McCowen. N Engl J Med 2010;363:2540-2546-National hospital glycemic practice guidelines are available yet most clinical staff are not familiar with methods recommended to safely achieve glucose targets2

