If the patient is to have a surgical procedure and the patient has been consented, then solely the sensor can be placed. The initial accuracy of CGM data is based on the length of time the sensor is in place and the CGM data has been shown to increase in accuracy with continued sensor wear. After the surgical procedure, the transmitter will be connected for communication of data to the receiver.

Sensor and transmitter will be removed before any CT, MRI or surgery. After procedure is complete, a new sensor can be placed if patient agrees.

Glucose Management

An Inpatient Glycemic Management Advanced Practice Registered Nurse Standardized Procedure (APN-S) will be followed (Appendix B: supplemental order set for subcutaneous insulin or PFO). The standardized procedure uses specific guidelines for the management of patients with diabetes within the hospital setting. The target goal for in-hospital blood glucose values are pre-prandial BG of 100-140 mg/dL and random BG less than 180 mg/dL.

Per PFO, if the initial POC testing value after alarm is 70-79 mg/dL then the patient will receive 15 gm glucose gel with follow up POC testing within 15 minutes. If the initial POC testing value after alarm is \geq 201 mg/dL anytime between 9pm (21:00) and 4am (04:00), and the patient has not received any insulin over the past three (3) hours, then patient will receive supplemental insulin dose, which is based on patient's current order of correction insulin. Communication will be ongoing between the advanced practice diabetes team, physician in charge of the patient's care as well as the patient's care team.

For Type 1 patients or Type 2 patients randomized in Intervention group, , CGM data will be used by APN to evaluate BG control of the patient every 24 hrs and/or earlier based on alarm CGM settings and rates of change arrows. The CGM device will be set to alarm if rate of change is trending towards hypoglycemia with a value of ≤ 90 mg/dL (arrow being shown will be , which means that if BG continues falling at this rate, BG could decrease up to 30 mg/dL in 15 minutes) or trending towards severe hyperglycemia with a value of ≥ 250 mg/dL (arrow being shown will be , which means that if BG continues rising at this rate, BG could increase up to 30 mg/dL in

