Appendix B

INSULIN, SUBCUTANEOUS ORDERS-SUPPLEMENTAL ORDERS ADULT, NON-PREGNANT PATIENTS

PATIENT NAME

DATE OF BIFTH (DOB)

MEDICAL RECORD NUMBER(MRN)

ACCT. NO/CSN

Orders preceded with a box must be checked to activate. All other orders are effective unless modified. Complete blanks to specify information not predefined. Initial each modification made to the order set, e.g., additions, deletions, strikeouts. Initial each internal page in bottom right corner. Statements in italics represent decision support for providers completing the order set; these statements are not part of the physician order(s). Provide corporate identification, sign, date and time last page.

Must be on Continuous Glucose Monitor Research Protocol and must be implemented in coordination with Diabetes APRN.

- Maintain current subcutaneous insulin order set and insure that it includes an HS correction option.
- 2. Implement the below orders in addition to currently active insulin order set.
- Obtain additional finger stick blood glucose as indicated per research protocol and/or directed by diabetes research team or designee.
- For any finger stick blood glucose between 70-79 mg/dL, give 1 tube (15 gm) glucose gel PO STAT or for patients unable to take PO, give D50W 25mL IVP STAT; recheck blood glucose 15 minutes after administration of glucose gel or D50W.
- If at any point after HS and before 4 am fingerstick blood glucose is greater than or equal to 200 mg/dL and no correction dose given in last three hours, administer correction dose per selected scale below.

Correction Coverage: Insulin Lispro (Humalog) subcutaneously per selected scale and blood glucose value:

Blood Glucose (Default Scale)	Insulin Scale				
	☐ Very Low	Low	□ Moderate	□High	
201-250 mg/dL	1 unit	2 units	3 units	4 units	
251-300 mg/dL	2 units	3 units	5 units	6 units	
301-350 mg/dL	2 units	4 units	6 units	8 units	
351-400 mg/dL	3 units	5 units	8 units	10 units	
Greater than 400 mg/dL	3 units	6 units	9 units	12 units	

6. Above orders to be discontinued when patient is discontinued from CGM research study.

Г	Prescriber Signature	Printed Name or Corporate ID				Date and Time
\vdash	Transcriber Signature	Printed Name or Corporate ID	Date and Time	RN Signature	Printed Name or Corporate ID	Date and Time
L						

PO 100-N\$8720-399\$W

S-INSCGM 100-NS8720-399SW (8/22/18)

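### A device allergy ends study participation, not just sensor use; this stops supplemental orders that need no sensor and puts the 7-day questionnaire in doubt (minor)

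*Combined protocol and SAP*

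**What the plan says.** The Potential Risks section describes allergy to a component of the sensor or transmitter as rare and then sets a rule with two parts: "If this occurs, then the device will be withdrawn and the patient will be discontinued from participation".

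The second part has a consequence in Appendix B. Item 6 of the supplemental orders reads "Above orders to be discontinued when patient is discontinued from CGM research study", and the header of the order set limits it to patients on the CGM research protocol. The orders that end are oral glucose gel or intravenous dextrose for a finger-stick of 70-79 mg/dL (item 4) and an overnight insulin correction (item 5).

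For control patients, whose CGM values are hidden from the care team, the Glucose Management section says "PFO will still apply during any time patient gets a POC from bedside RN per standard hospital procedures".

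On contact after discharge, the Follow-up section says "A follow-up questionnaire will take place within 7 days from discharge (including discharge date) to assess any adverse events" and to collect satisfaction with the stay and the device. It does not say whether a patient discontinued before discharge is included. Potential Risks adds "These possible expected risks will be assessed with the 1 week f/u call", but attaches this to site irritation, adhesive skin injury and itching after removal; allergy is treated in a later paragraph.

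**The concern.** The rule joins a clinical decision (no further sensor) to a research decision (no further participation). The first is plainly correct. The second removes a patient harmed by the device from orders that the protocol itself presents as a possible benefit of taking part, even for controls, and for no reason connected with the allergy.

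It may also remove that patient from the questionnaire on adverse events and device satisfaction. Aim 3 asks about acceptability. If patients who reacted to the device are not asked, the acceptability data lose some of the answers likely to be least favourable, and safety follow-up loses the cases it most needs.

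**Working it through.** The point is procedural and the plan gives no figure for it. The check is therefore mainly a comparison of sections, with a small count for scale.

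**1. Does leaving the study end the orders?** Yes. Potential Risks makes discontinuation from the study the result of an allergy. Appendix B item 6 makes that same event, and not removal of the sensor, the stopping point of the orders.

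**2. Do the orders need a sensor?** No.
- The Overview and Specific Aims apply the order set to all participants, and to any POC result of 70-79 mg/dL.
- Appendix B items 4 and 5 are written on finger-stick values.
- Control patients receive the orders on routine bedside POC tests.
- Only the extra POC tests prompted by a CGM alarm depend on the sensor.

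**3. Does the protocol elsewhere separate the device from participation?** Yes.
- The Adverse Events section records interruption or discontinuation of CGM and of the nurse-led glucose procedure as separate actions.
- Sensors also come off for CT, MRI, surgery or sensor failure, and none of these is said to end participation.

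**4. Is the questionnaire kept or cancelled?** Neither is stated. The wording is general (both type 2 groups are named), but no sentence covers discontinued patients.

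**5. What stays in place?**
- Appendix B item 1: "Maintain current subcutaneous insulin order set and insure that it includes an HS correction option". Item 2 makes the research orders an addition to that set.
- Below 70 mg/dL, hospital standing orders apply.
- Finger-sticks are regular care.
- Adverse events are charted with an outcome ("outcome (resolved, resolved with sequelae, ongoing, death").

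**6. Scale.** The documents give no allergy rate, and known adhesive allergy is an exclusion. I assume p = 0.5%, 1% and 2%; none of these comes from the documents.

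| Group | 0.5% | 1% | 2% |
|---|---|---|---|
| 110 type 2 G6: expected number, 110 × p | 0.55 | 1.10 | 2.20 |
| 53 usual care: 53 × p | 0.27 | 0.53 | 1.06 |
| 57 RT-CGM: 57 × p | 0.29 | 0.57 | 1.14 |
| At least one of 110: 1 − (1 − p)^110 | 42% | 67% | 89% |

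**7. Aim 2.** Its outcome is CGM readings, and none accrue after removal whatever the patient's study status. As an upper bound on lost precision, suppose affected patients were dropped altogether.
- The Sample Size section gives a 4.2-point difference, N = 110, alpha 0.05 and power 0.80, but no SD, so its power cannot be reproduced directly.
- Solving for the SD with a two-sided test and 55 per arm: 4.2 / [(1.960 + 0.842) × √(2/55)] = 7.86 points.
- At that SD, losing 2 of 110 gives power 0.793, and losing 4 gives 0.785.

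**The case against.** The strongest reply is that this is a CGM trial and the supplemental set is a research-only order. Ending participation when the device cannot be worn is coherent, and the patient returns to ordinary hospital care. The follow-up wording has no stated exception, sensors normally come off before discharge anyway, and the 1-week call already covers adhesive injury. Much of this stands. It is why the point is minor, and why the questionnaire can only be called in doubt, not cancelled. It does not remove the explicit two-part rule or its link to Appendix B.

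Some stronger readings are tempting and are not supported:

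- **That type 1 and intervention patients could keep the orders only in part.** A reader might infer this from "Per PFO, if the initial POC testing value after alarm is 70-79 mg/dL then the patient will receive 15 gm glucose gel". The Overview, the Specific Aims and Appendix B item 4 are not limited to tests after an alarm, so only the alarm-prompted tests are lost.
- **That cover is lost for 7 of 24 hours.** The 21:00-04:00 window is in the protocol body, but item 5, the order that actually ends, runs from bedtime to 4 am. It acts only if a POC test falls in that period, is high enough, and no correction dose was given in the past three hours. Routine POC is about four times a day, at times not stated.
- **That the 47 type 1 patients belong in the count.** Appendix C describes that subgroup's CGM data as standard of care, analysed by encounter. It is unclear that the research rule governed them.

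**Conclusion.** The point holds as a cheap improvement of minor weight. The rule is explicit, it ends orders that do not depend on the sensor, and it leaves follow-up uncertain in the few patients with a device allergy.

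The number affected is unknown; the 0.6 to 2.2 of 110 rests wholly on the assumed 0.5% to 2%. Even the denominator is uncertain: Appendix C describes the 110 as enrolled for at least 18 hours. If that was a condition for analysis, patients removed earlier for allergy would not be among them.

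A reader might infer that the patient is left untreated, or that the Aim 2 comparison is compromised. The documents support neither. The base insulin set and the standing orders below 70 mg/dL are not tied to participation. Both type 2 arms wear a sensor, so both are exposed to the event, and the power change above is within about two points.

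**What to change.** In Potential Risks, replace the discontinuation clause with: *CGM is stopped and not re-inserted; unless consent is withdrawn, the patient stays in the study for follow-up of the reaction to resolution, routine POC data to discharge and the 7-day questionnaire.*

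In Appendix B item 6, add: *After CGM is stopped for a device reaction, these orders continue on routine POC values unless the treating physician or APN stops them.* Keeping the patient in the study also satisfies the order-set header.

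For the G6 type 2 data already analysed, only reporting can change. State by arm how many patients were discontinued for a device allergy, among all randomised G6 patients and not only the 57 and 53 analysed.

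The cost is two sentences and one count per arm. POC values, adverse-event charting and the questionnaire already exist. The downside is minor extra chart extraction for a few patients without a sensor.

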Appendix A

From Scripps LMS
2014 Point of Care testing
(POCT) Nova Stat Strip Glucose

